Whenever this number is greater than 50%, then this stopping rule is met and further prolongation of the dosing interval in any subsequent cohort will cease. As an additional safety precaution, if individual stopping rules (eg, due to AEs) are invoked in 10 of the first 20 subjects to enroll in any cohort, further enrollment in that cohort will cease. Finally, the SMC retains the authority to stop further enrollment into a cohort at any time for any reason. If any of these conditions transpire, all remaining subjects, including those ongoing subjects in the terminated cohort, and future subjects, will be administered AR101 300 mg at the longest interval tolerated by a previous cohort.

*Assumptions = Up to approximately 500 ARC003 completers (having received active or placebo in ARC003 at a 3:1 ratio) are projected for recruitment into ARC004. This assumes a loss of 15% of the randomized ARC003 population due to attrition, AEs, etc. Thus, the planned sizes for the ARC004 cohorts is as follows, though the actual number may vary due to recruitment:

- Cohort 1 = 120, prespecified
- Cohort 2 = 50, prespecified
- Cohort 3 = 175, distributed equally across Cohorts 3A, 3B, 3C
- Group 1 = 130 (25% of ARC003 enrollment, accounting for 5% dropout)

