4.1. SAFETY POPULATION

The primary population of analysis for all analyses will be the Safety population. The Safety population will consist of all subjects who receive at least one dose of study treatment during ARC004.

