10.3. ADVERSE EVENTS

Treatment-emergent adverse events (TEAEs) will be summarized excluding symptoms recorded during the food challenges. The AE summaries will report AEs and in-clinic dosing symptoms.

If symptoms are recorded as part of an anaphylactic reaction, only the single anaphylactic reaction event will be summarized and not the individual symptoms.

All reported adverse events (AEs) will be classified into System Organ Class (SOC) and Preferred Term (PT) using Medical Dictionary for Regulatory Activities (MedDRA) version 19.1. The 5-point CoFAR severity grading scale was used for coding allergic reactions. The 3-point Muraro grading scale was used for grading the severity of anaphylactic reactions. The 5-point CTCAE severity grading scale was used for coding all other adverse events.

In Group 1, treatment-emergent adverse events are defined as those AEs with onset after the first dose of study product in ARC004 and no more than 30 days after the last dose of study product. In Group 2, as all patients are assumed to be continuing AR101 from study ARC003, all reported adverse events with onset no more than 30 days after the last dose of study product will be defined as treatment-emergent. Non treatment-emergent AEs will be included in subject listings, but not summarized. An additional summary of age group 18-55 will be included for the safety population for the overall AE summary and SAE summary.

Summaries that are displayed by system organ class and preferred terms will be ordered by descending incidence of system organ class and preferred term within each system organ class. Summaries displayed by preferred term only will be ordered by descending incidence of preferred term. Summaries of the following types will be presented:

- Overall summary of number of unique TEAEs and treatment-emergent serious adverse events (TESAEs), subject incidence of TEAEs and TESAEs meeting various criteria and exposure-adjusted incidence rates of TEAEs and TESAEs meeting various criteria, where exposure incidence rates are defined as the total number of events divided by the total number of subject-years at risk during the study period;
- Subject incidence of TEAEs by MedDRA system organ class and preferred term;
- Exposure-adjusted event rates for the most frequent TEAEs (i.e., TEAEs occurring in $\geq 5\%$ of the Safety Population) by MedDRA preferred term;

Sponsor: Aimmune Therapeutics, Inc.

Protocol: ARC0004

Version: Version 1.0, 10Jul2019

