- Subject incidence of treatment-related AEs by MedDRA system organ class, and preferred term;
- Exposure-adjusted event rates for the most frequent treatment-related AEs (i.e., treatment-related AEs occurring in $\geq 5\%$ of the Safety Population) by MedDRA preferred term;
- Subject incidence of grade ≥ 3 severity TEAEs by MedDRA system organ class and preferred term;
- Subject incidence of grade ≥ 3 severity treatment-related AEs by MedDRA system organ class and preferred term;
- Subject incidence of TESAEs by MedDRA system organ class and preferred term;
- Subject incidence of TEAEs leading to discontinuation of study product by MedDRA system organ class and preferred term;
- Subject incidence of TEAEs associated with Epinephrine use by MedDRA system organ class and preferred term.
- Subject incidence of hypersensitivity TEAEs by MedDRA system organ class and preferred term, where hypersensitivity TEAEs are all TEAEs from the in-clinic dosing CRFs and all TEAEs indicated as an allergic reaction on the AE CRF
- Subject incidence of hypersensitivity treatment-related AEs by MedDRA system organ class and preferred term;
- Exposure-adjusted event rates for the most frequent hypersensitivity TEAEs (i.e., hypersensitivity TEAEs occurring in $\geq 5\%$ of the Safety Population) by MedDRA preferred term;
- Subject incidence of TEAEs associated with nonstudy product food allergen exposure by MedDRA system organ class and preferred term; and
- Subject incidence of TEAEs leading to early withdrawal by MedDRA system organ class and preferred term

At each level of summarization (e.g., any AE, system organ class, and preferred term), subjects experiencing more than one TEAE will be counted only once within each study period. In the summary of TEAEs by severity grade, subjects will be counted once at the highest severity reported at each level of summarization.

Sponsor: Aimmune Therapeutics, Inc.

Protocol: ARC0004

Version: Version 1.0, 10Jul2019

Adverse event data will be presented in data listings by age group (4-17 years and 18-55 years), group/cohort, subject, study period, and event. Serious TEAEs; Serious DBPCFC AEs; severe, life-threatening, or fatal adverse events; anaphylactic reactions; and AEs leading to discontinuation, reduction, or interruption of the study product will be presented in separate data listings.

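### The 5% whole-population cut in SAP 10.3 can leave a preferred term concentrated on nondaily dosing without a term-specific exposure-adjusted rate

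*SAP*

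**What the plan says.** SAP 10.3 lists three exposure-adjusted tables by preferred term, each restricted to terms reaching 5% of the Safety Population:

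- all treatment-emergent events: "Exposure-adjusted event rates for the most frequent TEAEs (i.e., TEAEs occurring in" at least that share;
- treatment-related events: "Exposure-adjusted event rates for the most frequent treatment-related AEs (i.e., treatment-related AEs occurring in" at least that share;
- hypersensitivity events: "Exposure-adjusted event rates for the most frequent hypersensitivity TEAEs (i.e., hypersensitivity TEAEs occurring in" at least that share.

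SAP 4.1 fixes the denominator: "The Safety population will consist of all subjects who receive at least one dose of study treatment during ARC004". Read literally, it pools Group 1, including its escalation and up-dosing, with every Group 2 cohort.

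Two other parts of SAP 10.3 carry no 5% cut. The overall summary gives "exposure-adjusted incidence rates of TEAEs and TESAEs meeting various criteria", defined as events per subject-year at risk in the study period. The incidence tables cover every term, for example "Subject incidence of treatment-related AEs by MedDRA system organ class, and preferred term". SAP 6.1 and SAP 10 split event summaries by cohort and dosing period, with separate QOD and BIW columns.

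**The concern.** The primary objective concerns alternative maintenance intervals and the primary endpoint is the frequency of treatment-related events. No formal comparisons are planned (SAP 6.4), so the safety of nondaily dosing will be judged from the descriptive tables.

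A whole-population cut picks the terms that are common across all treated subjects. Most of the planned subjects never leave daily dosing, so a term can be fairly common on QOD or BIW and still miss the cut. A reader then has only subject incidence for that term, across columns whose planned lengths differ up to 14-fold. The aggregate rate for the column allows for exposure but cannot show which reaction differs by interval.

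**Working it through.** **Inputs.** Planned sizes from Protocol 7.8.3: Cohort 1, 120; Cohort 2, 50 ("Cohort 2 = 50, prespecified"); Cohort 3, 175 split equally over three arms; Group 1, 130. Accrual of about 400 is assumed in Protocol 9.4 and SAP 2.4; the protocol synopsis caps enrolment at about 500. Planned period lengths from SAP 2.3: QOD 4 weeks, BIW 24, Cohort 1 QD 28, Cohort 3A QD 56.

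**The plan's own safety figure.** The documents give no figure for the 5% cut. Their one safety-precision statement is an 80% chance of seeing at least one event at 4 per 1,000 in 400 subjects: 1 − 0.996^400 = 0.799. It reproduces.

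**Size of the cut.** Planned total = 120 + 50 + 175 + 130 = 475. Subjects needed = smallest whole number at or above 0.05 × N. Planned nondaily subjects = 50 + (2/3) × 175 ≈ 167.

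| N | Subjects needed | Share of 167 nondaily | Share of Cohort 2 (50) if none elsewhere |
|---|---|---|---|
| 400 | 20 | 20/167 = 12.0% | 20/50 = 40% |
| 475 | 24 | 24/167 = 14.4% | 24/50 = 48% |
| 500 | 25 | 25/167 = 15.0% | 25/50 = 50% |

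The 167 is held fixed across rows. The third column assumes that the term does not occur outside nondaily dosing.

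**With some background.** Take N = 475 and an assumed background b in the 425 subjects outside Cohort 2. The largest expected Cohort 2 count still omitted is 23 − 425b:

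- b = 1%: 23 − 4.25 = 18.75, or 37.5% of Cohort 2
- b = 2%: 23 − 8.5 = 14.5, or 29%
- b = 3%: 23 − 12.75 = 10.25, or 20.5%

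**Why crude incidence does not replace the rate.** Planned exposure per subject in 3A is 56/24 = 2.3 times that on BIW and 56/4 = 14 times that on QOD. An illustration with assumed counts, one event per affected subject and full planned periods:

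- Cohort 2 on BIW: 5/50 = 10.0%. Subject-years = 50 × 24/52 = 23.1. Rate = 5/23.1 = 0.22 per year.
- Cohort 3A on QD: 7/58 = 12.1%. Subject-years = 58 × 56/52 = 62.5. Rate = 7/62.5 = 0.11 per year.

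Incidence is lower on BIW while the rate is about twice as high. The term has 12 subjects in all, 12/475 = 2.5%. With up to 11 more elsewhere it would still stand at 23, below the cut, so the table that would show the reversal omits it.

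**With the cut applied by column.** A term would enter at 3 of 50 in Cohort 2 (0.05 × 50 = 2.5) and at 6 of about 117 in combined Cohorts 3B and 3C (0.05 × 117 = 5.85).

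**The case against.** A reader might infer that these are the only tables that allow for unequal exposure, or that a QOD- or BIW-specific term gets no rate of any kind. The documents do not support that. The overall summary in SAP 10.3 gives uncut exposure-adjusted rates, and an omitted term's events count there in their own cohort and period. The term itself remains in the uncut incidence tables by cohort and regimen period and in the listings. Anaphylactic reactions (SAP 10.14) and epinephrine episodes (SAP 10.13) have their own tables by cohort and period. Exposure duration is summarised by cohort and study period (SAP 10.1), so a reader can roughly rescale an incidence.

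A reader might also infer that the rate tables are biased towards showing no nondaily signal. That is not shown. Protocol 1.4.1 says that essentially all events in earlier oral immunotherapy studies were allergy related, and Protocol 7.2 describes allergic symptoms as frequent during dose escalation. Counting Group 1 up-dosing therefore helps familiar allergic terms to pass. Nothing in the SAP confines a passing term's rate to the daily columns, so a higher BIW rate of a common reaction would be displayed. Nor does the amount of daily dosing time drive the cut, which counts subjects.

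The 40% to 48% figures need zero occurrences outside Cohort 2, although Cohorts 3B and 3C also receive QOD and BIW. The 12% to 14% figures are the fairer measure.

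Finally, the study is descriptive, and a frequency cut on a table of most frequent events is a display choice. That limits the weight of the point but does not remove it. The gap is confined to terms more common on nondaily dosing than elsewhere, and those terms bear directly on the study's question.

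**Conclusion.** The point stands as a minor one and the change is a cheap improvement. Under the literal SAP wording, a term can affect up to 23 of 475 subjects, all on nondaily dosing (23/167 = 13.8%), and have no term-specific exposure-adjusted rate. It would be visible only as crude incidence over periods of 4 to 56 weeks, as listed events, and within an aggregate rate. The primary endpoint, the overall frequency of treatment-related events, is not affected.

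Confidence is moderate. The calculation rests on planned rather than actual cohort sizes and on reading the denominator as all treated subjects. SAP 10 tabulates most safety data for ages 4 to 17, and the SAP does not say whether the 5% is judged within that subset. If so, the required count would be somewhat lower but would still pool all cohorts. The table shells are in a separate document and could settle the matter.

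**What to change.** In all three SAP 10.3 bullets, replace the Safety Population condition with: occurring in at least 5% of subjects in any displayed group/cohort/regimen column. Print the event count and subject-years beside each rate. Because each table's columns carry their own denominators, this also settles which age subset the cut uses.

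No new data or methods are needed. The cost is longer tables and some imprecise rates. The 4-week QOD column of Cohort 2 has about 50 × 4/52 = 3.8 subject-years, so 3 events give about 0.8 per year with an exact 95% interval of roughly 0.2 to 2.3. Showing counts and subject-years makes that imprecision plain.

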7.1 Definitions

All safety events observed under this protocol are reported through the electronic data capture (EDC) system for the duration of the study. Some safety events arising under certain defined conditions are recorded on specific forms as follows.

- Any allergic symptoms observed during in-clinic dosing will be recorded directly on the Escalation/In-Clinic Dosing Form (also referred to as a Study Product Administration Form), and are not recorded on an AE form (to avoid duplicate reporting) unless the event is considered an SAE. These symptoms are, however, by definition, AEs ([Section 7.2](#)) and will be reported as such in the database.
- Non-serious AEIs are reported on an AEI form and include anaphylaxis episodes meeting the criteria below, accidental food allergen exposures, GI AEs resulting in prolonged disruption of dosing, AEs associated with the use of epinephrine, and severe AEs ([Section 7.3.3](#)). They are not to be reported on an AE form (to avoid duplicate reporting) unless the event is considered an SAE, as defined below ([Section 7.3.2](#)).
- If any safety event meets the definition of an SAE (whether or not related to dosing), it will also be recorded on an AE/SAE form.
- Skin prick test reactions are not considered AEs unless the reaction, or a complication from the procedure, is considered an SAE, as defined below ([Section 7.3.2](#)).
- Food challenge reactions that occur in the clinic are captured on study specific forms and are not reported on an AE form (to avoid duplicate reporting) unless the event is considered an SAE, as defined below ([Section 7.3.2](#)).
 - As study product is not used in the DBPCFCs, no AEs occurring from Screening DBPCFC can be treatment-related (referring to treatment with study product).
 - For food challenge reactions that occur at the Exit DBPCFC, it will also usually be the case that study product was not the cause of the reaction, as study product is not used in the challenge. There is, however, the possibility that dosing with study product in the days prior to Exit DBPCFC could contribute to a reaction encountered during the challenge. The investigator must determine if dosing with study product in the days prior to Exit DBPCFC likely contributed to any observed reaction. If so, the investigator should indicate the level of the relatedness, and provide a brief explanation as to the manner in which prior dosing with study product was thought to be contributory.

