7.3.3.5 Adverse Events Associated with Use of Epinephrine

Adverse events may result in epinephrine use. Upon awareness of such an event, site staff will report it within 24 hours using the AEI form, independent of severity or relatedness, or

whether it was administered in the CRC or at home. If the epinephrine was used as part of an allergic reaction that meets criteria for anaphylaxis, an accidental food allergen exposure, an AE featuring a severe symptom, or an SAE, the use need not be reported separately. The intent of this AEI is to capture events that may be occurring that do not fall into 1 of these other categories.

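### SAP 10.3 defines hypersensitivity TEAEs by source form and leaves out the AEI form, so non-serious severe, epinephrine-treated or anaphylactic home reactions can be missing from the three hypersensitivity tables

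*SAP*

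**What the plan says.** Protocol 7.1 assigns safety events to forms.

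- **Reactions to clinic doses:** "Any allergic symptoms observed during in-clinic dosing will be recorded directly on the Escalation/In-Clinic Dosing Form". The same bullet says these are AEs and will appear as AEs in the database.
- **Non-serious events of interest:** "Non-serious AEIs are reported on an AEI form and include anaphylaxis episodes meeting the criteria below". The list goes on to accidental food exposures, GI events with prolonged dosing disruption, and "AEs associated with the use of epinephrine, and severe AEs". For all of these: "They are not to be reported on an AE form (to avoid duplicate reporting) unless the event is considered an SAE".
- **Epinephrine use:** Protocol 7.3.3.5 again names the AEI form, whether the drug was given in clinic or at home.

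SAP 10.3 describes its general AE tables by content: "The AE summaries will report AEs and in-clinic dosing symptoms". Where symptoms belong to an anaphylactic reaction, "only the single anaphylactic reaction event will be summarized and not the individual symptoms". Only the hypersensitivity definition is written in terms of forms: "hypersensitivity TEAEs are all TEAEs from the in-clinic dosing CRFs and all TEAEs indicated as an allergic reaction on the AE CRF". Three outputs use that term: subject incidence of hypersensitivity TEAEs, subject incidence of hypersensitivity treatment-related AEs, and exposure-adjusted rates of the most frequent hypersensitivity TEAEs. The SAP nowhere names the AEI form as a data source.

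**The concern.** Taken together at face value, the two rules leave a gap in the middle of the severity range. A mild home reaction goes on the AE form and is counted. A serious reaction goes on the AE/SAE form and is counted. A non-serious home reaction that was severe, needed epinephrine or met the anaphylaxis criteria goes on the AEI form, which the definition does not read.

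Home reactions matter in this study. Under protocol 3.1.5 only the first two doses at each of the longer intervals (BIW, QW, QOW) are supervised, every-other-day dosing may start at home, and later doses are taken at home. Tables meant to describe allergic reactions to study product could therefore miss the clinically most important non-serious ones.

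**Working it through.** The point has no numerical input. The check is to trace each kind of reaction outside a food challenge from form to table.

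| Reaction | Form if protocol 7.1 is followed literally | Inside the SAP hypersensitivity definition? |
|---|---|---|
| Home; not severe, no epinephrine, not anaphylaxis | AE form | Yes, if flagged allergic |
| Clinic dosing, any severity | In-clinic dosing form | Yes |
| Serious, any location | AE/SAE form | Yes, if flagged allergic |
| Home, non-serious; severe, epinephrine-treated or anaphylactic | AEI form, kept off the AE form | No |

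The protocol text that points the other way changes only the last row:

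1. Protocol 7.2 puts each symptom of a multi-symptom allergic reaction on its own line of the AE eCRF, with a yes/no query on whether it is an allergic reaction. That is the flag the SAP definition uses. The sentence does not cover a reaction with a single symptom.
2. Protocol 7.5.1 describes one multi-screen AE eCRF through which all AEs are submitted.
3. The last sentence of protocol 7.1 refers to a combined AE/AEI/SAE form set.

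On that reading the last row becomes Yes. The same SAP sentence therefore gives two different event sets, depending on which protocol section governs data entry.

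For the other SAP 10.3 tables, the scope is AEs plus in-clinic dosing symptoms, and all reported AEs are coded. No form is named. An anaphylactic reaction is counted as one event within these summaries. Non-serious home reactions drop out of them only if the AEI records are not merged into the AE dataset, and the documents do not say whether they are.

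On size, the documents give no count or share of events that would sit only on the AEI form. The one numerical safety statement (protocol 9.4 and SAP 2.4) is an 80% probability of seeing at least one AE at a rate of 4 per 1,000 among about 400 subjects. It reproduces: 1 − (1 − 0.004)^400 = 0.799. As illustration only, suppose a table captures a share c of an event type with that true rate. The probability of seeing at least one is then 1 − (1 − 0.004c)^400:

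| Assumed share captured, c | Probability of at least one |
|---|---|
| 1 | 0.799 |
| 0.90 | 0.764 |
| 0.75 | 0.699 |
| 0.50 | 0.551 |
| 0.25 | 0.330 |
| 0 | 0 |

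The value of c is assumed throughout; nothing in the documents fixes it.

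**The case against.** The best defence is that 7.1 is a data-entry rule whose stated aim is to avoid duplicates, not an analysis exclusion. AEIs are AEs by definition, since protocol 7.3.3.1 calls an anaphylaxis event an AE. SAP 10.3 also plans tables that presuppose these events are in the AE data: TEAEs associated with epinephrine use, TEAEs associated with food allergen exposure, and listings of severe events and anaphylactic reactions. SAP 10.13 breaks epinephrine episodes down by the severity, seriousness and relatedness of the associated AE and by home or study site, which needs a linked AE record. If the AE CRF in the SAP means the single multi-screen eCRF of protocol 7.5.1, nothing is lost.

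Most of this stands, and it limits the point in three ways.

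- A reader might infer that the primary endpoint (treatment-related AEs) and the grade 3 or higher tables hold only serious and in-clinic events. The documents do not support that, because those tables have no form restriction.
- A reader might infer that the AEI form is the only place where these reactions are recorded. Protocol 7.2 and 7.5.1 leave that open.
- A reader might infer that the events vanish from the report. They do not: SAP 10.14 summarizes anaphylaxis, 10.13 epinephrine use, 10.4 food exposures and 10.5 at-home dosing symptoms.

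The defence does not remove the form-based wording of the hypersensitivity definition, which conflicts with 7.1 as written. Nor do the other outputs fully cover the gap. Severe home reactions that are neither anaphylactic nor epinephrine-treated have no dedicated AEI-based summary, and neither the severe-event listing nor the at-home symptom summary names its source form.

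**Conclusion.** The point holds for the three hypersensitivity tables. If sites followed protocol 7.1 literally and the SAP definition is programmed as written, up to all non-serious home reactions that were severe, epinephrine-treated or anaphylactic would be absent from them. For the general AE, treatment-related and grade 3 or higher tables the loss is conditional on AEI records not being merged into the AE dataset.

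The number of events affected cannot be derived from the documents. Nor can the direction of any distortion between dosing regimens. A reader might infer that a regimen with more such reactions would look safer, but that needs both the unmerged reading and a difference between regimens in the share of events lost, and the documents establish neither. The conclusion rests on the text alone; the CRF layout and dataset specifications, which could settle the recording route, are not part of the documents.

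**What to change.** 1. In SAP 10.3, define hypersensitivity TEAEs by event: any treatment-emergent allergic reaction, including anaphylaxis, recorded on the AE/SAE form, the AEI form or the in-clinic dosing form. Apply the same definition to all three hypersensitivity outputs.
2. In the same section, state that the AE analysis dataset is the union of those forms, with a de-duplication rule (for example on subject, onset date and time, and term). Keep the existing rule that an anaphylactic reaction counts once.
3. Before database lock, check that every epinephrine-treated event in SAP 10.13 and every anaphylactic reaction in SAP 10.14, food challenges aside, has its counterpart in the AE dataset, and resolve mismatches.
4. Reconcile the recording instructions in protocol 7.1 with 7.2 and 7.5.1, so that it is clear which form holds a non-serious event of interest.

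The cost is SAP wording and one de-duplication step. No additional data are needed. If the records are already merged, the change only documents what is done.
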